The study is using the label-recommended dose and schedule for RCC (50 mg QD 4 weeks on, 2 weeks off). Dose interruption and/or dose modification in 12.5-mg increments or decrements is recommended based on individual safety and tolerability, as per label recommendations. If 50 mg QD cannot be tolerated, the next dose level is 37.5 mg QD. Dose can be further reduced to 25 mg QD. Once toxicity has been alleviated, doses should be re-escalated stepwise to 37.5 mg and then 50 mg. Subjects requiring a dose below 25 mg QD should be permanently discontinued from study treatment. During each 6-week cycle, subjects will be off of treatment for 2 weeks. If an additional dose interruption for more than 2 weeks is required, the Sponsor should be consulted (Table 11).

Table 11 Dose Modification Guidelines for AEs Potentially Associated with Sunitinib Treatment

Toxicity	NCI CTCAE Grade	Sunitinib
Hypertension See Section 5.6.2 for monitoring/management of treatment-related hypertension.	SBP \leq 150 mm Hg and / or DBP \leq 100 mm Hg	Continue at the same dose level Antihypertensive treatment maybe initiated
	SBP >150 mm Hg but < 160 mm Hg and / or DBP >100 mm Hg but < 105 mm Hg	Continue at the same dose level, and institute new or additional antihypertensive medication if not on maximal antihypertensive treatment, or Reduce by 1 dose level if on maximal antihypertensive treatment.
	SBP >160 mm Hg and / or DBP > 105 mm Hg	Hold dose and adjust antihypertensive medication to achieve BP controlled to SBP \leq 150 mm Hg and DBP \leq 100 mm Hg. Resume at the same dose level or 1 level reduced. Note: If sunitinib dosing is temporarily interrupted, subjects receiving antihypertensive medications should be monitored closely for hypotension.
	Recurrent hypertensions following previous dose reduction	Repeat dose interruption and/or dose reduction by one lower dose level. Permanently discontinue if hypertension is severe and persistent despite antihypertensive treatment and dose interruption, or experience hypertensive crisis, transient or permanent neurological deficit related to uncontrolled hypertension.

Toxicity	NCI CTCAE Grade	Sunitinib
Proteinuria	Dipstick negative or 1+	Continue at the same dose level.
	If dipstick shows $\geq 2+$, perform 24-hour urine protein or UPC. Dosing may continue while waiting for test results	
	Urine protein < 3 g/24 hr or UPC < 3	Continue at the same dose level.

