	Urine protein ≥ 3 g/24 hr or UPC ≥ 3	Hold until urine protein is < 3 g/24 hr or UPC <3. Restart with 1 dose level lower Permanently discontinue if urine protein cannot reduce to < 3 g/24 hr or UPC <3 after dose reduced to 25 mg daily
Prolongation of QTc Interval:	480 < QTc < 500 msec	Continue study treatment; monitor as clinically indicated.
	QTc ≥ 500 msec	Permanently discontinue and follow-up per protocol.
Diarrhea/Colitis	Grade 1-2	Continue at the same dose level
	Grade 3	Continue and dose reduce by 1 dose level Follow the guidelines as in non-hematologic toxicities
	Grade 4	Follow the guidelines as in non-hematologic toxicities
Hemorrhage /Bleeding: Investigate and document underlying etiology of the bleeding	Grade 1	For hemoptysis, interrupt study treatment and evaluate underlying causes. Resume at the discretion of the investigator. For other Grade 1 hemorrhage/bleeding events, continue at the current dose; monitor as clinically indicated.
	Grade 2	For pulmonary or GI bleed (other than hemorrhoidal bleeding), Permanently discontinue and follow-up per protocol. For other Grade 2 hemorrhage/bleeding events, interrupt study treatment until the AE resolved to \leq Grade 1. Restart at 1 dose level lower
	Grade 3 or 4	Permanently discontinue and follow-up per protocol.
Hyperthyroidism	Grades 1-2	Continue at the same dose level
	Grade 3	Grade 3 toxicities controlled with symptomatic medications, or Grade 3 asymptomatic biochemistry (other than abnormal liver tests) laboratory abnormalities: may continue at the same dose level or reduce by one dose level per Investigator judgment
	Grade 4	Hold until recovery to Grade ≤ 1 or BL. Restart at 1 dose level lower.
Hypothyroidism	All grades	Dose can be continued while thyroid replacement therapy is instituted
Isolated AST/ ALT or bilirubin elevation	Grade 1	Continue at the same dose level
	Grade 2	Hold until recovery to Grade ≤ 1 or BL. Restart at same dose level.
	Grade 3 or 4	Hold until recovery to Grade ≤ 1 or BL. Restart at 1 dose level lower.
	ALT/AST >3xULN concurrent with total bilirubin > 2xULN (excluding Gilbert syndrome)	Permanently discontinue and perform virology and serology tests to evaluate the causes

Toxicity	NCI CTCAE Grade	Sunitinib
Non-hematologic Toxicities, Laboratory Abnormalities and/or Other Drug Related Toxicities suspected to be contributed to sunitinib	Grade 1 - 2	Continue at the same dose level

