	Grade 3 or intolerable grade 2	Withhold dose until toxicity is Grade \leq 1 or has returned to BL Resume treatment at the same dose level. ^a If the toxicity recurs with Grade 3 severity (or intolerable Grade 2) at the discretion of the investigator, reduce the dose by 1 level.
	Grade 4	Withhold dose until toxicity is Grade \leq 1 or has returned to BL, then reduce the dose by 1 level and resume treatment, or discontinue at the discretion of the investigator. ^a
		Permanently discontinue sunitinib for: 
 Any life-threatening adverse event. Subjects with the following events: CHF,^b pancreatitis, necrotizing fasciitis, nephrotic syndrome and thrombotic microangiopathy), RPLS, and arterial thrombosis/ ischemia Nausea, vomiting, or diarrhea persist at Grade 3 or 4 despite maximal medical therapy.
Hematologic Laboratory Abnormalities	Grade 1-2	Continue at the same dose level.
	Grade 3	Withhold dose until toxicity is Grade \leq 2 or has returned to BL, then resume treatment at the same dose level. ^c If the toxicity recurs with Grade 3 severity, at the discretion of the investigator, reduce the dose by 1 level.
	Grade 4	Withhold dose until toxicity is Grade \leq 2 or has returned to BL Restart with 1 dose level lower. ^c

^a Subjects who develop Grade 3 hypophosphatemia or Grade 4 hyperuricemia without clinical symptoms may continue study treatment without interruption at the discretion of the investigator.

^b Subjects should be carefully monitored for clinical signs and symptoms of CHF while receiving sunitinib. Assessment of LVEF should be considered as clinically indicated per sunitinib label and standard of care.

^c Subjects who develop Grade 3 or 4 lymphopenia may continue study treatment without interruption. Complicated neutropenia includes duration of Grade 4 longer than 7 days or concurrent fever or infection.

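### Table 11 gives two incompatible instructions for a first Grade 3 diarrhea event on sunitinib: continue one dose level lower, or withhold and resume at the same dose

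*Combined protocol and SAP*

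**What the plan says.** Section 5.2.2 directs sites to follow the guidelines for a study drug when an adverse event is assessed as associated, or potentially associated, with it. For sunitinib these are in Section 5.2.2.4 and Table 11.

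- **Diarrhea/Colitis, Grade 3:** "Continue and dose reduce by 1 dose level Follow the guidelines as in non-hematologic toxicities".
- **Diarrhea/Colitis, Grade 4:** the cross-reference only, "Follow the guidelines as in non-hematologic toxicities".
- **Non-hematologic, Grade 3 or intolerable Grade 2 (the row referred to):** withhold until Grade 1 or less, or until the toxicity "has returned to BL Resume treatment at the same dose level". Reduction comes later: "If the toxicity recurs with Grade 3 severity (or intolerable Grade 2) at the discretion of the investigator, reduce the dose by 1 level".
- **Permanent discontinuation, in the same non-hematologic block:** "Nausea, vomiting, or diarrhea persist at Grade 3 or 4 despite maximal medical therapy".

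The text above the table presents interruption, dose change or both as a recommendation guided by individual tolerability, in 12.5 mg steps. It sets a floor ("Subjects requiring a dose below 25 mg QD should be permanently discontinued from study treatment") and provides for recovery ("Once toxicity has been alleviated, doses should be re-escalated stepwise to 37.5 mg and then 50 mg").

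**The concern.** The Grade 3 diarrhea cell gives one action and then calls in a rule that gives another. For a first event they disagree on both decisions a site must make: whether to interrupt, and what dose comes next. Two sites reading the same cell in good faith could treat the same event in opposite ways. One would keep the subject on drug, at a lower dose, during Grade 3 diarrhea. The other would stop the drug and later restore the full previous dose.

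The stakes are subject safety and uniform management of the control arm. There is also a record-keeping consequence. Section 8.11 requires deviations from protocol-directed administration to be reported, and with two directed actions a site that complies with one departs from the other.

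**Working it through.** There is no planned figure to reproduce. The check sets the two instructions side by side, works out the dose each gives, and asks whether anything else in the document settles the choice.

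**1. Doses after a first Grade 3 event.** Inputs from Section 5.2.2.4: step 12.5 mg; levels 50, 37.5 and 25 mg; floor 25 mg.

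| Current dose | Continue, one level lower | Withhold, then same dose |
|---|---|---|
| 50 mg | 50 − 12.5 = 37.5 mg, no break | 0 mg, then 50 mg |
| 37.5 mg | 37.5 − 12.5 = 25 mg, no break | 0 mg, then 37.5 mg |
| 25 mg | 25 − 12.5 = 12.5 mg, below the floor, so discontinue | 0 mg, then 25 mg |

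At the upper two levels the next dose differs by 12.5 mg per dosing day: 12.5/50 = 25%, or 12.5/37.5 = 33%.

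**2. Cumulative dose.** Take a subject on 50 mg and count 28 scheduled dosing days from onset, with *h* of them held under the second instruction and no re-escalation.

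- First instruction: 28 × 37.5 = 1,050 mg.
- Second instruction, held doses made up: 28 × 50 = 1,400 mg, which is 350 mg more.
- Second instruction, held doses lost: (28 − *h*) × 50 mg. The difference from the first is 350 − 50*h*. It is zero at *h* = 7, and at *h* = 14 it is 350 mg less.

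Figure 3 in Section 5.2.3.4 allows both patterns. In scenario A the remaining doses are completed. In scenario B, where the hold runs into the off-treatment period, dosing resumes only at the next cycle. The sign of the net difference is therefore indeterminate.

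**3. Does anything settle the choice?**

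- The Table 11 footnotes do not. Footnote a concerns hypophosphatemia and hyperuricemia, b heart failure, and c lymphopenia and neutropenia.
- The diarrhea stop rule applies only to diarrhea that persists despite maximal therapy, not to a first event.
- Reading the cell as two successive steps does not help. No order or trigger is printed, continuing contradicts withholding, and reducing contradicts resuming at the same dose.
- Table 8 does not help either. Its Grade 3 diarrhea row for axitinib has only the cross-reference, but the rule it leads to lets axitinib continue at the same or a reduced dose.

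**4. Hypertension rows (minor).** In Tables 8 and 11 the middle band ends below 160 systolic and below 105 diastolic, and the hold band starts above those values. A reading of exactly 160 or exactly 105 belongs to neither. The and/or wording also lets one reading, such as 170/90, meet both the continue band (through its diastolic value) and the hold band (through its systolic value). Both rows cite Section 5.6.2, general supportive care; hypertension management is Section 5.6.1.

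**The case against.** The best defense is that Section 5.2.2.4 frames dose changes as recommended according to individual tolerability and allows interruption, reduction or both. On that view the diarrhea row, being specific, governs the first event, and the cross-reference serves recurrence and persistence. That reading is workable, and the stop rule for persistent diarrhea does appear only in the non-hematologic block. But it is not printed. The specific row itself calls in the general rule without limit, and Section 5.2.2 tells sites to follow the guidelines.

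A second defense is that a line break, bullet or "or" was lost when the PDF was read. This cannot be excluded. It is tempting to rule it out by noting that the table prints its choices with a criterion, as in the middle hypertension band ("if not on maximal antihypertensive treatment, or Reduce by 1 dose level if on maximal antihypertensive treatment"). That argument fails: the next band offers the same dose or one level lower with no criterion. What can be said is that a bare "or" would still leave two opposite actions and no basis for choosing.

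Three stronger readings are not supported:

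- *The first instruction is unworkable at 25 mg.* The floor sentence already gives the outcome, which is discontinuation.
- *The control arm is systematically under- or over-dosed.* The direction depends on the length of the hold and on whether held doses are made up, and Section 5.2.2.4 provides for later re-escalation.
- *The efficacy comparison is compromised.* The documents give no sunitinib diarrhea rate, and alpha, event targets and the intention-to-treat PFS and OS analyses do not depend on this cell.

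**Conclusion.** The point holds as a defect in an operative dosing rule. For a first Grade 3 diarrhea event on sunitinib the table directs both continuation at a lower dose and withholding with return to the same dose, with no order of priority. The size per subject is 37.5 mg without a break versus a hold and then 50 mg; 25 mg without a break versus a hold and then 37.5 mg; or discontinuation versus a hold and then 25 mg. How many subjects are affected cannot be estimated from the documents, and the net cumulative dose difference has no fixed sign.

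The conclusion assumes that the cell's wording is as extracted. It does not depend on knowing which instruction the sponsor intended. The hypertension items are real but small: single boundary values, an overlap between bands, and a pointer to the neighboring section.

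**What to change.** Keep one instruction in the Table 11 Grade 3 diarrhea cell.

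- **Default:** delete the instruction to continue at one level lower. The cell then holds only the cross-reference, like the Grade 4 row beneath it, and the non-hematologic withhold and stop rules apply.
- **Alternative:** if the sponsor's clinical team intends continuation at a reduced dose, state that this row overrides the non-hematologic first-event rule, and limit the cross-reference to recurrence and persistence.

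The choice is clinical and belongs to the sponsor.

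In the hypertension rows of Tables 8 and 11, assign exactly 160 systolic and exactly 105 diastolic to a band (for example, hold at ≥160 and/or ≥105), state that the higher band governs, and change the cross-reference to Section 5.6.1.

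The cost is one cell in Table 11, the band limits and one cross-reference in each of two tables, and a notice to sites. Randomization is complete at N = 861 (Section 8.9), so the change reaches only subjects still on treatment. It still matters for them, because Table 5 continues sunitinib until progression is verified by central review or further confirmed by the investigator.

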5.2.3 Timing of Dose Administration

Study treatments should begin on the day of randomization or within 3 days of randomization in both treatment arms. Study treatments and relevant safety assessments are cycle based. The day that the first dose of study treatment is received by each subject denotes Cycle 1 Day 1 (C1D1).

For the combination arm, each treatment cycle is 21 days, which is based on a Q3W dosing schedule of pembrolizumab. C1D1 of the combination arm should start when the subject can receive the first dose of pembrolizumab. The first dose of axitinib should start on the same day when first dose of pembrolizumab is administered, if possible, or start on the following day. For the sunitinib arm, each treatment cycle is 42 days. Study treatment will continue in 21-day or 42-day cycles, for the combination arm and sunitinib arm, respectively, until study treatments are permanently discontinued for the subject. The clinical visits and assessments are detailed in Section 6 – Trial Flow Chart.

5.2.3.1 Pembrolizumab Administration

Pembrolizumab will be administered on Day 1 of each 21-day cycle (± 3 days) starting on C1D1. Pembrolizumab should be administered after all pre-dose study procedures and assessments have been completed as detailed on the Trial Flow Charts in Section 6. Pembrolizumab should be administered as a 30-minute IV infusion. Sites should make every effort to target infusion timing to be as close to 30 minutes as possible. However, given the variability of infusion pumps from site to site, a window of -5 min and $+10$ min is permitted (i.e., infusion time is 30 minutes: -5 min/ $+10$ min). The Pharmacy Manual contains specific instructions for the preparation and administration of pembrolizumab.

5.2.3.2 Axitinib Administration

Axitinib will be taken orally BID, at approximately the same time in the morning and evening each day with approximately 12 hours between the 2 doses. Axitinib should be taken continuously with exception of dose interruptions due to drug-related AEs or intolerance (see Section 5.2.2).

Axitinib tablets may be administered with or without food. Tablets must not be crushed, split or dissolved and subjects should be instructed to swallow the study medication whole without manipulation or chewing of the medication prior to swallowing.

Subjects must be instructed that if they miss a dose or vomit any time after taking a dose, they must not “make it up” with an extra dose, but instead resume subsequent doses as prescribed. Any missed dose may be taken later up to 3 hours before the next scheduled dose, otherwise, it should be skipped and dosing should resume with subsequent doses as prescribed. Subjects must be instructed to record all doses (missed or vomited doses) in a dosing diary supplied by the site. If doses are missed or vomited, this must be indicated in the source documents and case report forms (CRFs). If a subject inadvertently takes 1 extra dose during a day, the subject should not take the next dose. A dosing diary will be provided to subjects to record dosing details for axitinib.

5.2.3.3 Sunitinib Administration

The first dose of sunitinib administration denotes C1D1 for each subject. Each treatment cycle of sunitinib is 42 days \pm a 3-day window. Within each treatment cycle, sunitinib will be administered orally once daily for 4 weeks and then off treatment for 2 weeks.

Sunitinib can be administered with or without food. Capsules must not be crushed, split, or dissolved and subjects should be instructed to swallow the study medication whole without manipulation or chewing of the medication prior to swallowing.

Subjects must be instructed that if they miss a dose or vomit any time after taking a dose, they must not “make it up” with an extra dose, but instead resume subsequent doses as prescribed. Subjects must be instructed to record all doses (missed or vomited doses) in a dosing diary supplied by the site. If doses are missed or vomited, this must be indicated in the source documents and CRFs. A dosing diary will be provided to subjects to record dosing details for sunitinib.

5.2.3.4 Dosing Schedules with Study Treatment Interruptions

In general, subjects in the combination arm should be maintained on an every 21-day (Q21D) treatment and assessment schedule from C1D1 until both treatment(s) are permanently discontinued. In the events that treatment-related AEs require dose interruption or discontinuation of one study drug only, the other study drug should be continued as scheduled, so as the safety assessments. Sometimes, both drugs need to be withheld for a treatment-related AE until causality is clear or until AE improves. Figure 2 depicts a few dose interruption scenarios that may be encountered in the combination arm.

[figure not shown]

Figure 2 Dose Interruption Scenarios in the Combination Arm

Scenario (A), at C2D1 visit, an immune-related AE is identified that requires pembrolizumab to be on hold but not axitinib, axitinib is then continued. A worsening of hypertension led to brief dose interruption of axitinib during cycle 1 and Cycle 3. Scenario (B), axitinib was interrupted from C1D10 for an axitinib-specific toxicity, subject still comes for C2D1 visit for safety assessment and received Cycle 2 dose of pembrolizumab on schedule. Scenario (C), pembrolizumab has been on hold after Cycle 1 due to a drug-related AE, pembrolizumab can be resumed on C3D10, and the subject may start C4D1 ahead of time and continue the Q21D treatment and safety assessment cycle with this new starting point.

Similarly, subjects who are randomized to the sunitinib arm should be maintained on a 42-day treatment and assessment schedule as much as possible. Figure 3 depicts a few dose interruption scenarios for the sunitinib arm.

[figure not shown]

Figure 3 Dose Interruption Scenarios for Sunitinib

(A), if a dose interruption is required within the 28-day treatment period of a cycle, the remaining doses should be completed followed by 2-weeks' off treatment period. (B) If dose interruption extends to the off treatment period and AE resolved, subject should complete the remaining off treatment period and resume treatment at the next cycle per schedule. (C) If dose interruption extends to the treatment period of the following cycle, subject should resume with a new 42-day cycle and continue the 4 weeks on treatment and 2 weeks off treatment schedule and the required assessments.

5.2.4 Trial Blinding

This is an open-label trial; therefore, the Sponsor, investigator and subject will know the treatment administered.

5.3 Randomization

Treatment randomization will occur centrally using an interactive voice response system / integrated web response system (IVRS/IWRS). There are 2 treatment arms. Subjects will be assigned randomly in a 1:1 ratio to the pembrolizumab plus axitinib combination arm or the sunitinib monotherapy arm.

5.4 Stratification

Prior to randomization subjects will be stratified according to the following factors:

1. International Metastatic RCC Database Consortium (IMDC) risk group: favorable versus intermediate versus poor risk groups [2, 3]
2. Geographic region: North America versus Western Europe versus "Rest of the World."

IMDC risk category for each subject is determined first by assessing 6 risk factors as shown in [Table 12](#).

Table 12 IMDC Risk Evaluation

Assessments	Risk Factor
Baseline Karnofsky Performance Status	< 80%
Interval between initial diagnosis of RCC to start of first-line systemic treatment for advanced disease (note for this study, date of randomization will be used as the start of first-line systemic treatment)	< 1 year
Baseline Hemoglobin	< Lower limit of normal
Baseline Platelet Count	> Upper limit of normal
Baseline Corrected Calcium ¹	> Upper limit of normal
Baseline Neutrophil	> Upper limit of normal
The IMDC risk group is determined by totaling the existing risk factors per subject.	
IMDC Risk Group	IMDC Category
Favorable	No risk factors
Intermediate	1 or 2 risk factors
Poor	3 or more risk factors
1. Corrected calcium can be calculated based on the following formula: $\text{Corrected calcium (mg/dl)} = 0.8 \times [4.0 - \text{subject's albumin (g/dl)}] + \text{subject's calcium (mg/dl)}.$ A subject's corrected calcium will be compared with the upper limit of normal of institution serum calcium.	

Sites will be provided with a worksheet that utilizes these criteria for calculating the IMDC risk group. The group will be entered into the IVRS as a stratification factor at the time of randomization.

